8.3.3. Humoral Immune Responses

HIV-specific Binding Antibody ELISA Assays will be performed to detect serum or plasma IgG and IgA binding antibodies to HIV-1 gp120, in particular to the V1V2 loops. Capture antigens will include V1V2 sequences from both subtype AE and Subtype B HIV-1 Env (gp70V1V2 92TH023 and gp70V1V2 Case A2), and HIV-1 Env gp120 proteins matched to sequences in AIDSVAX® B/E without the gD tag and with an 11 amino acid N-terminal deletion, represented as gp120 A244gD- D11 and gp120 MNgD- D11. Durability of IgG response will be assessed for each participant by estimating the decline in log10 IgG from peak to 6 and 12 months post final vaccination.

Neutralizing Antibody Assays will be measured as a function of reductions in luciferase (Luc) reporter gene expression after a single round of infection in TZM-bl cells using high throughput analysis. Stocks of molecularly cloned envelope-pseudotyped viruses have been prepared by transfection in 293T/17 cells (American Type Culture Collection) and titrated in TZM-bl cells. This assay has been formally optimized and validated and was performed in compliance with Good Clinical Laboratory Practices (GCLP), including participation in a formal proficiency testing program. Tier 2 neutralization was assessed using a panel of 11 pseudoviruses, and a global panel.

Antibody Profiling will be conducted to assess antibody breadth and correlation of Fc receptor usage with antibody function. The current capacity for Antibody Profiling is the assessment of over 300 samples in one experiment. The beads presenting the HIV antigens will be distributed robotically in a high-throughput manner into 384 well plates. Similarly, the samples will be diluted robotically and incubated with the beads. Detection reagents will be added to the wells after washing. These detection reagents are inclusive of subclass, isotype and Fc receptor usage. Therefore, in one well, we will be able to capture 900 to 1000 data points from a single sample, and over 250,000 data points per experiment that will allow evaluation of the humoral immune response to these vaccine strategies.

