### 4.5.3. Selection and Timing of Dose for Each Participant

This is a three-dose study, with participants receiving the assigned study product of interest at Month 0 (Day 1), Month 1 (Day 29), and Month 2 (Day 57).

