### **4.7. Immunogenicity Variables**

Vaccine-induced immune responses will be assessed in study participants as detailed in the SOE.

Humoral responses will be assessed by HIV-specific binding antibody assays, HIV-specific neutralizing antibody assays, and non-neutralizing antibody function assays at baseline and days

1, 15, 29, 42, 57, 70, 168, and 336. Durability of IgG response will be assessed for each participant by estimating the decline in log10 IgG from peak to 6 and 12 months post final vaccination.

Measurement of CD4+ and CD8+ T-cell effector function will be evaluated through response by cytokines such as IFN- $\gamma$  and IL2. CD4+ lymphoproliferation will be measured with the CFSE assay. Innate immunity (e.g., NK cells) will be assessed by quantifying ADCC and ADCP, determining NK cell phenotype using various flow cytometric panels, cytokine array assays to characterize the type of cytokines elicited by this vaccine regimen with or without adjuvants, by the assessment of gene expression by DNA microarray and related techniques, and other related assays. B cell responses will be characterized in blood and in diverse anatomical compartments (provided by sigmoid biopsies and lymph nodes biopsies) in a subset of participants. Host gene transcription profile and signature to vaccine antigens will be assessed by RNA sequencing and related techniques.

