## 8. IMMUNOGENICITY EVALUATION

### 8.1. Primary Immunogenicity Analyses

All summaries and analysis of immunogenicity data will be presented for the Immunogenicity Population. Humoral and cellular immunogenicity will be assessed primarily through descriptive statistics. Primary immunogenicity endpoints are IgG binding antibodies to g120 and antigen-specific CD4 and CD8 T cell responses.

The magnitude of plasma IgG (antigen-specific) responses will be measured by the endpoint titer at study weeks 0, 2, 4, 6, 8, 10, 24 and 48. Means or Geometric mean titers (GMTs) will be calculated for each group as appropriate based on the distribution, at each visit, and the per-participant peak response across all visits. Additionally, 95% confidence intervals (CI) will be computed using bootstrapping, or alternative methods. Results will be presented as exponentiated GMT and 95% CI. The distributions of GMTs will be compared across all vaccination groups via ANOVA (null hypothesis that the medians across all groups do not differ) at the 5%-statistical significance level, or using the Kruskal-Wallis test if ANOVA assumptions are violated; in the event Kruskal-Wallis testing is implemented the shape and scale uniformity across groups will be assessed for validity and results interpretation. Pairwise comparisons of GMT responses between dose groups at follow-up time points will be evaluated using a two-sided Mann-Whitney U test, with a Bonferroni-Holm step-down for adjusting p-values for multiple comparisons. Where necessary and appropriate, False Discovery Rates (FDR) will be calculated and reported using the Benjamini-Hochberg (BH) method.

The number and percentage of positive IgG responses to binding targets will be presented by vaccination group and visit based on input from the laboratory team. Differences between vaccinations groups will be evaluated using Fisher's exact test, or chi-squared tests.

Durability of IgG response will be assessed for each participant by estimating the decline in  $\log_{10}$  IgG from peak to 6 and 12 months (weeks 24 and 48 respectively) post final vaccination.

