## APPENDIX 1: ADDITIONAL TABLES AND FIGURES

**Table 1: Participant Disposition by Vaccination Group**

Participant Disposition	200 µg ALFQ (N=X)		100 µg ALFQ (N=X)		50 µg ALFQ (N=X)		All Participants (N=X)	
	n	%	n	%	n	%	n	%
Screened	--	--	--	--	--	--	--	--
Enrolled/Randomized	x	100	x	100	x	100	x	100
Received Study Vaccination Dose 1 (Visit 1, Day 1)	x	xx	x	xx	x	xx	x	xx
Completed Visit 2 (Day 15)	x	xx	x	xx	x	xx	x	xx
Received Study Vaccination Dose 2 (Visit 3, Day 29)	x	xx	x	xx	x	xx	x	xx
Completed Visit 4 (Day 43)	x	xx	x	xx	x	xx	x	xx
Received Study Vaccination Dose 3 (Visit 5, Day 57)	x	xx	x	xx	x	xx	x	xx
Completed Visit 6 (Day 58-9)	x	xx	x	xx	x	xx	x	xx
Completed Visit 7 (Day 64)	x	xx	x	xx	x	xx	x	xx
Completed Visit 8 (Day 71)	x	xx	x	xx	x	xx	x	xx
Completed Visit 9 (Day 169)	x	xx	x	xx	x	xx	x	xx
Completed Visit 10/Exit (Day 337)	x	xx	x	xx	x	xx	x	xx
Phone Follow-up #1 (Day 365)	x	xx	x	xx	x	xx	x	xx
Phone Follow-up #2 (Day 393)	x	xx	x	xx	x	xx	x	xx
Note: N = Number of randomized participants								

Table 2: Summary of Demographic and Baseline Characteristics by Vaccination Group

Variable	Characteristic	200 µg ALFQ (N=X)		100 µg ALFQ (N=X)		50 µg ALFQ (N=X)		All Participants (N=X)		p-value
		n	%	n	%	n	%	n	%	
Age	18-29	x	xx	x	xx	x	xx	x	xx	
	30-39									
	40-49									
	50+									
Age, years	Mean									
	Standard Deviation									
	Median									
	Q1 (25 th percentile)									
	Q2 (75 th Percentile)									
Gender	Male									
	Female									
	Transgender									
Sex at birth	Male									
	Female									
	Undifferentiated									
Level of Education										
	Primary education									
	Secondary education									
	Undergraduate degree									
	Graduate									
	Other									
Race	White									
	Black or African American									
	Asian									
	American Indian/Alaskan Native									
	Native Hawaiian or Other Pacific Islander									
	Multiracial									
	Other									
Ethnicity	Non-Hispanic/Latino									

Variable	Characteristic	200 µg ALFQ (N=X)		100 µg ALFQ (N=X)		50 µg ALFQ (N=X)		All Participants (N=X)		p-value
		n	%	n	%	n	%	n	%	
	Hispanic/Latino									

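### The IgG decline measure is labelled 6 and 12 months after the final vaccination, but its two draws fall 16 and 40 weeks after that dose

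*SAP*

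**What the plan says.** SAP 8.1 takes the IgG "endpoint titer at study weeks 0, 2, 4, 6, 8, 10, 24 and 48". The same section then defines durability as the decline in log10 "IgG from peak to 6 and 12 months (weeks 24 and 48 respectively) post final vaccination". SAP 4.7 (Immunogenicity Variables) gives the time points without week numbers, as "IgG from peak to 6 and 12 months post final vaccination". Protocol 8.3.3 has the same definition: "decline in log10 IgG from peak to 6 and 12 months post final vaccination".

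SAP 4.5.3 places the three doses at "Month 0 (Day 1), Month 1 (Day 29), and Month 2 (Day 57"). The disposition shell (SAP Appendix 1, Table 1) lists "Completed Visit 9 (Day 169"), "Completed Visit 10/Exit (Day 337") and "Phone Follow-up #2 (Day 393"). The Visit Week row of the schedule (Protocol Table 1; SAP schedule of events) puts Day 169 at week 24, Day 337 at week 48 and Day 393 at week 56. Protocol 4.7 (End of Study Definition) says that clinic visits run for 10 months after the final vaccination and that the last two contacts are by telephone.

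**The concern.** The section uses one pair of week numbers with two different origins. In the titer schedule, weeks 24 and 48 count from dose 1. In the durability definition the same weeks are said to follow the final dose, which is given in study week 8. Both cannot be true.

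Durability is a named component of the secondary IgG endpoint (Protocol Section 3; SAP 3.2.2), listed beside magnitude and area under the curve. A report that follows SAP 8.1 would present 16- and 40-week persistence as 6- and 12-month persistence after the last dose. A reader comparing the adjuvant with other regimens would credit the response with lasting longer than was observed. The SAP has no table shell for decline from peak, so this text is the only source for the label.

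**Working it through.** **Inputs**
- Dose 1 on Day 1 and dose 3 on Day 57 (SAP 4.5.3).
- Visit 9 on Day 169 and Visit 10 on Day 337 (SAP Appendix 1, Table 1; schedule of events).
- Windows of ±7 days: dose 3 on Days 50–64, Visit 9 on Days 162–176, Visit 10 on Days 330–344 (SAP Table S6).

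**1. Reproduce the plan's label.** Counting from dose 1:
- Visit 9: (169 − 1)/7 = 24 weeks, and 168/28 = 6 months of 28 days.
- Visit 10: (337 − 1)/7 = 48 weeks, and 336/28 = 12 months of 28 days.

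The label is exact from the first dose, using the 28-day months of the dosing schedule.

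**2. Count from the final dose, as the text says.**
- Visit 9: 169 − 57 = 112 days; 112/7 = 16 weeks; 112/28 = 4 months.
- Visit 10: 337 − 57 = 280 days; 280/7 = 40 weeks; 280/28 = 10 months.

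The 10 months agrees with the length of clinic follow-up in Protocol 4.7.

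**3. Size of the overstatement.**
- 24 − 16 = 8 weeks; 24/16 = 1.5.
- 48 − 40 = 8 weeks; 48/40 = 1.2.

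**4. Visit windows.**
- Visit 9: from (162 − 64)/7 = 14 to (176 − 50)/7 = 18 weeks.
- Visit 10: from (330 − 64)/7 = 38 to (344 − 50)/7 = 42 weeks.

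The shortfall is therefore 24 − 18 = 6 to 24 − 14 = 10 weeks, and 48 − 42 = 6 to 48 − 38 = 10 weeks. Within the windows, no combination brings a draw closer than 6 weeks to its label.

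**5. Take the label literally.**
- 24 weeks after the final dose: 57 + 168 = Day 225. No visit is scheduled there.
- 48 weeks after the final dose: 57 + 336 = Day 393. This is the second phone contact; the blood-volume rows of the schedule end at Visit 10.

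**6. Calendar months instead of 28-day months.** Six months is 182.6/7 = 26.1 weeks and twelve is 365.25/7 = 52.2 weeks. The gaps widen to 26.1 − 16 = 10.1 and 52.2 − 40 = 12.2 weeks.

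**The case against.** Four points can be made for the plan.

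- **The right samples would be used anyway.** SAP 8.1 names weeks 24 and 48, and only Visits 9 and 10 match. This stands: the defect is in what the result is called, not in how it is computed. A value at Day 225 could also be interpolated between the two draws, but no such method is specified, and Day 393 lies beyond the last draw.
- **Little depends on it.** Immunogenicity is mainly descriptive. Protocol 9.6.3 and SAP Table 14 assess durability by area under the curve on visit week, which is correctly anchored, and titers are tabulated by visit. This limits the reach of the error. It does not make the label correct for a measure that SAP 8.1 itself calls durability.
- **The calendar-month figures use a convention that the plan does not use here.** That is fair. The 8-week difference, on the plan's own months, is the main figure.
- **The window ranges describe the schedule, not what happened.** Also fair. Protocol 6.3 allows vaccination outside the window, and the SAP revision history records that it occurred, so individual intervals may fall outside the ranges above.

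**Conclusion.** The label is wrong as written. The two draws are 16 and 40 weeks after the scheduled final dose, not 24 and 48, and neither the visit windows nor a different month length reconciles them. No scheduled sample can give a value at 12 months after the final vaccination.

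The effect is confined to the stated interval for this one measure. All arms share the schedule, so comparisons among them are not biased by it. The effect on the reported decline cannot be sized, because the documents give no decay data.

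The 16 and 40 weeks assume that dose 3 was given on Day 57. The immunogenicity population needs only one dose. For a participant who stopped after dose 2 on Day 29, the intervals would be (169 − 29)/7 = 20 and (337 − 29)/7 = 44 weeks. This is a further reason to anchor the measure on study week.

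**What to change.** In SAP 8.1 and SAP 4.7, define the measure as the drop in log10 IgG between peak and study weeks 24 and 48. Add that these are 16 and 40 weeks after the final vaccination as scheduled on Day 57, and delete the reference to 6 and 12 months after it. While SAP 4.7 is open, align its sampling days 42, 70, 168 and 336 with the schedule's 43, 71, 169 and 337.

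Protocol 8.3.3 carries the same wording. It can be corrected at the next amendment, or the change can be noted in the clinical study report, the two routes that Protocol 9.2 gives for departures from the statistical plan.

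Optionally, add one descriptive row with the actual days from last dose to each of the two draws, since some vaccinations were out of window. The dates are already collected.

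The cost is a wording change in two SAP sections, which SAP Section 11 allows for before unblinding. No blood draw, sample, test or area-under-the-curve calculation changes.

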9.6.3. Immunogenicity Analysis

The primary immunogenicity endpoint is the magnitude of immune response to the endpoint titer of plasma IgG. Immune response over time (durability) will be assessed by the positive incremental area under the curve (AUC) based on a graph with log endpoint titer on the y-axis and visit week on the x-axis. Summary statistics at specific time points of interest will also be provided using the mean and standard deviation (or median and interquartile range (IQR) as appropriate). Primary comparisons may use a 2-sample t-test with an unadjusted alpha of 0.05. When differences are found, pairwise comparisons between vaccination groups will be made using the Holm-Bonferroni method and a 5% significance threshold for the adjusted p-values.

Further exploratory comparisons may be performed and adjusted for multiplicity as appropriate. Secondary immunogenicity endpoints will entail primarily descriptive analyses. In general, continuous outcomes will be assessed using summary statistics such as the mean, median, standard deviation and IQR. Binary responses will be described using frequencies and percentages. Changes from baseline may be assessed within groups using paired t-tests (or Wilcoxon signed rank as appropriate) or McNemar's test for binary outcomes. Changes over

time between groups may be evaluated using longitudinal models with unstructured covariance matrices where possible or covariance strictures selected as appropriate for the observed data.

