**DATE: 22 January 2024**

**SAP Revision History**

Revision Date	Analyst	Revisions/Justification
01Feb2023	[name]/[name]	Additional sensitivity analyses due to unanticipated vaccinations occurring out of study window
21 December 2023	[name]/[name]	Detailing interim Analysis plans for Humoral Immunity and dose response
11 January 2024	[name]/[name]	Finalized edits and Added CONSORT example diagram
18 January 2024	[name]/[name]	Clarified Interim analysis specifications for cellular response

Trial Initiation Date: first participant screened 08 Sept 2022

Trial Completion Date: last participant visit 29 Oct 2024

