### 3.3. Study Definitions and Defined Variables

The baseline value will be defined as the last value obtained prior to the first vaccination. Individual antibody endpoint titers will be reported with values of  $C^*2^k$ , where  $k=0, 1, 2, \dots$

and C may vary depending on the dilutions used for a given assay. Values below each assay's limit of detection will be imputed as one-half the limit of detection. For analysis, the geometric mean of replicates for each sample will be computed and used as the response for all subsequent calculations, where applicable.

Immune response over time will be assessed by the positive incremental area under the curve (AUC) based on a graph with the analysis value (e.g., log endpoint titer) on the y-axis and visit week on the x-axis.

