Measurements that occur outside of the scheduled protocol-specified assessment time-windows will be flagged and assigned to the intended study visit. These measurements will be included in the primary analyses; sensitivity analyses will be conducted to determine whether the results differ when these measurements, which occurred outside of the scheduled protocol-specified assessment time-windows, are excluded. Although multiple measurements occurring within the same assessment window are not anticipated to be an issue, if such an event occurs the analytic approach will be determined based on the specific measure and accounting for clinical rationale and standard approaches in the literature. For example, the minimum value, maximum value, earliest value or latest value may be considered for sensitivity analyses.

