### Area under the Response Curve

Mean area under the curve (AUC) can be used to represent the time and population averaged immune response from week 0 to week 10. Time will be measured in days since first injection and reflect the date of sample collection (rather than visit number). Immunogen response distribution will be assessed for each visit for overall homogeneity of response pattern independently for each group. Time-normalized values will be calculated for AUC (denoted as nAUC) to account for differences in follow-up time due to early drop-out or missing data. Individual nAUC may be calculated via the trapezoidal method as:

$$\frac{1}{T} \sum_{i=1}^m \frac{Y_{i,j}}{T} + \frac{\tilde{T}}{2} \frac{1}{T}$$

Where  $\frac{1}{T} \sum_{i=1}^m \frac{Y_{i,j}}{T}$  is the normalized AUC for an individual;  $T$ =total observation time for individual  $i$ ;  $Y_{i,j}$ =humoral response of individual  $i$  at time  $j$ ,  $m$ =number of timepoints for individual  $i$ ,  $t_{i,j}$ =time in days for individual  $i$  at time  $j$ .

If the data reflects apparent inflection points, a cubic spline function may be used to estimate the functional form of the response data, and the nAUC may be derived using the definite integral of

the response curve from v0 to v10 to account for the data's inflection tendencies. Estimation of nAUC may also be derived through applications of a linear mixed effect model following methods outlined in Alexandre (2021) for group level effects, with or without the inclusion of additional covariates.

ANOVA will be used to assess differences in AUC between groups. Normality assumptions for immunogenicity marker AUC will be assessed. If strong departures from normality are observed data will be transformed to achieve normality; log transformations will be prioritized but other transformations will be explored as appropriate for optimal fit. In the case where normality transformations perform poorly, a Kruskal-Wallis analysis will be used incorporating appropriate adjustments for equivalence testing.

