Total immune responses over time will be assessed by the positive incremental area under the curve (AUC). An AUC curve will be constructed with raw, unlogged endpoint titers on the y-axis and visit week on the x-axis (week 0 to week 48). AUC will be logged after calculation from raw values. For comparability between participants with different numbers of samples (visits) available, these values will be scaled (normalized) by the week of the last available sample. If no sample is available for visits other than the first and last, no explicit imputation will be done, and the AUC will be calculated based on available samples. Log AUC will be analysed similarly to the visit-by-visit titers and presented as mean AUC and 95% CI.

The magnitude of CD4+ and CD8+ T-cell effector function and polyfunctionality will be evaluated through response by cytokines such as IFN- $\gamma$  and IL2. The frequencies of CD4 or CD8 T cells responding to each test antigen with IFN- $\gamma$  and/or IL2 will be calculated using the following categories: all IFNy+, all IL2+, IFNy and IL2+, IFNy or IL2+. Descriptive statistics will evaluate the distribution of CD4+ and CD8+ responses and polyfunctionality scores by vaccination group and visit. Differences in CD4+ and CD8+ responses between vaccination groups at each visit will be evaluated using Kruskal-Wallis tests, and pair-wise comparisons of

particular visits will be performed with two-sided Mann-Whitney U test, with a Bonferroni-Holm step-down for adjusting p-values for multiple comparisons.

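### The final IgG AUC is timed by nominal visit week while off-window samples stay under their intended visit, so it is mistimed for anyone sampled off the nominal day; the interim AUC already uses actual days

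*SAP*

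**What the plan says.** **Final AUC.** SAP 8.1 puts "endpoint titers on the y-axis and visit week on the x-axis (week 0 to week 48". The definition in SAP 3.3 has the same horizontal axis ("visit week on the x-axis"), and Protocol 9.6.3 agrees ("log endpoint titer on the y-axis and visit week on the x-axis"). Whether the titer axis is logged differs between these places, but that is a separate matter. SAP 8.1 measures the "endpoint titer at study weeks 0, 2, 4, 6, 8, 10, 24 and 48", which is the fixed visit-week row of the schedule of events. The AUC is then divided by the week of the last available sample and logged. SAP 8.1 does not say whether that divisor is nominal or actual.

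**Off-schedule samples.** Under SAP 5.5, measurements outside the windows "will be flagged and assigned to the intended study visit" and stay in the primary analyses. A sensitivity analysis leaves them out. SAP 8.3 allows an optional per-protocol repeat, which also works by exclusion.

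**Interim AUC.** SAP 5.6.1 takes the opposite choice: "Time will be measured in days since first injection and reflect the date of sample collection (rather than visit number".

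**Conduct.** The reason given for the SAP revision of 01Feb2023 is "Additional sensitivity analyses due to unanticipated vaccinations occurring out of study window". Protocol 6.3 lets the PSRT permit a vaccination outside its window, and Protocol 7.2 ends further vaccination when a dose is missed by more than 15 days.

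**The concern.** An AUC is titer integrated over time. If every sample is plotted at its nominal week, the result equals the AUC over real time only for participants seen on the nominal days. Anyone else gets intervals that are too long or too short, and the longest intervals (weeks 10 to 24 and 24 to 48) carry most of the area.

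The trial's own windows can produce this. The window table in SAP 5.5 uses fixed study days: dose 3 on days 50 to 64 and Visit 8 on days 68 to 74. A dose 3 given on day 64 and sampled 14 days later falls on day 78. That sample is out of window and would be filed as week 10. Samples inside a window but off the nominal day are affected too, and nothing flags them.

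At stake is the AUC comparison between ALFQ doses, one part of a secondary endpoint. The SAP gives no reason for using real time at the interim and nominal time at the end.

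**Working it through.** The documents state no AUC value or timing error, so there is no figure of theirs to reproduce. Two of their inputs do check: (day - 1)/7 for days 1, 15, 29, 43, 57, 71, 169 and 337 gives exactly weeks 0, 2, 4, 6, 8, 10, 24 and 48, and 10/48 = 20.8%, the follow-up fraction quoted for the interim.

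**Assumptions.** The trapezoid rule is used; the SAP names it only for the interim AUC. Raw titers are used, as in SAP 8.1. Profiles are invented, at the eight weeks above:
- A: 50, 200, 400, 12800, 6400, 51200, 6400, 1600
- B (slower decay): 50, 200, 400, 6400, 3200, 25600, 12800, 6400
- C (faster decay): 50, 400, 800, 25600, 6400, 51200, 1600, 400

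Titers are held fixed and only the times move, which isolates the axis.

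**Formula.** Sum over intervals of (time gap) × (mean of the two titers above baseline), divided by the last sampling time.

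**Profile A, nominal weeks.** Titers above baseline are 0, 150, 350, 12750, 6350, 51150, 6350, 1550. The interval areas are 150 + 500 + 13,100 + 19,100 + 57,500 + 402,500 + 94,800 = 587,650; divided by 48 this is 12,243. The value is the same whatever the collection dates.

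**Profile A, actual times.**
- Dose 3 and Visit 8 14 days late, Visits 9 and 10 on calendar (times 0, 2, 4, 6, 10, 12, 24, 48): 150 + 500 + 13,100 + 38,200 + 57,500 + 345,000 + 94,800 = 549,250; /48 = 11,443. Nominal/actual = 1.070.
- The same delay with all later visits shifted (0, 2, 4, 6, 10, 12, 26, 50): 606,750; /50 = 12,135. Ratio 1.009.
- Visit 9 28 days late (week 28): 686,850; /48 = 14,309. Ratio 0.856.

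**Nominal/actual ratio of normalised AUC, all profiles.**

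| Timing | A | B | C |
|---|---|---|---|
| In window: Visit 8 -3, Visit 9 +7, Visit 10 -7 days | 0.946 | 0.975 | 0.936 |
| In window: Visit 8 +3, Visit 9 -7 days | 1.044 | 1.022 | 1.050 |
| Dose 2 14 days late, all later visits shift | 1.041 | 1.041 | 1.039 |
| Dose 3 14 days late, Visits 9 and 10 on calendar | 1.070 | 1.056 | 1.043 |
| Dose 3 14 days late, all later visits shift | 1.009 | 1.024 | 0.980 |
| Dose 3 28 days late, Visits 9 and 10 on calendar | 1.150 | 1.119 | 1.089 |
| Visit 9 28 days late | 0.856 | 0.934 | 0.834 |
| Visit 9 28 days early | 1.203 | 1.076 | 1.249 |

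The largest error is about 0.10 on the log10 scale. For context only, the plan's SD of 0.2 and detectable difference of 0.202 were set for peak titer, not AUC.

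**The exclusion check.** SAP 8.1 joins whatever samples remain. In profile A, dropping week 24 replaces 402,500 + 94,800 with 19 × 52,700 = 1,001,300, so the area rises from 587,650 to 1,091,650 (+86%; +20% in B, +115% in C). Dropping week 10 replaces 57,500 + 402,500 with 8 × 12,700 = 101,600, giving 229,250 (-61%).

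**The normaliser.** If the area were on actual time but the divisor nominal, the all-shifted case above would be inflated by 50/48 = 1.042 from that mismatch alone. Both must be on one scale.

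**The case against.** The strongest reply is that this hardly matters for inference. AUC is logged before comparison, titers are read in two-fold steps (0.30 log10 each), and a 7% error is 0.029 log10. If a quarter of one arm had an error of about 5% (0.022 log10) and nobody else did, the arm mean would move by about 0.005. Coarse sampling after week 10 is a larger distortion: for a profile with an 8-week half-life, trapezoid interpolation overstates the smooth area by about 15%, and re-timing leaves that in place. All of this stands and sets the severity.

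There is also an estimand argument. Visit week aligns participants on the regimen, whereas days since first injection make the AUC depend on when the boost was given: the profile A participant drops from 12,243 to 11,443 at identical titers. That is a real trade-off, although the SAP has already accepted it at the interim.

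The interim mismatch alone proves little. The interim AUC uses four visits to week 10 and the final uses eight to week 48, so they would differ on any common axis.

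A reader might go further and infer that a late dose 3 always overstates AUC. The documents do not support that. It holds in these profiles if Visits 9 and 10 stay on the calendar, but if all later visits shift the error shrinks and in profile C changes sign. The documents do not say which happens. A reader might also infer that delays cluster in the higher-dose arm and bias the comparison. Nothing in the documents gives the number, size or arm distribution of off-schedule doses or samples.

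**Conclusion.** The point holds as a minor improvement. The three textual facts are clear: nominal week in the final AUC, off-window samples kept under the intended visit, and actual days in the interim AUC. The mistiming follows arithmetically for anyone off the nominal day.

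Its size rests on invented profiles and the trapezoid rule: about -6% to +5% inside the windows and -2% to +7% for a dose 14 days late. Only gross departures do worse: +9% to +15% for a dose 3 28 days late with later visits on calendar, and -17% to +25% for Visit 9 off by 28 days. No such departures are documented. If deviations are balanced across arms, the effect is mainly noise; a between-arm bias is possible but not shown.

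The exclusion analyses test the influence of off-window samples but do not correct their timing. Because they can move a participant's AUC far more than the timing error, a discrepancy they produce could be misread as fragility.

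**What to change.** - In SAP 3.3 and 8.1, compute the final AUC on actual days since first injection at sample collection, as in SAP 5.6.1. Divide by the actual day of the last sample, so that area and normaliser share one scale.
- Keep the visit-week AUC as a sensitivity analysis. For the AUC, use it ahead of the exclusion analyses to judge the effect of timing.
- Record the departure from Protocol 9.6.3 in SAP section 11 before unblinding, and in a protocol amendment or the clinical study report as Protocol 9.2 requires.

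The cost is small. Collection date and time are already on the specimen tracking form (Protocol 6.4), and the programming change is minor. The downsides are a documented deviation from the protocol wording and an AUC that reflects when the boost was actually given; the retained visit-week version shows how much that matters.
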